If the child's developmental age is 7 or greater ([see above](#)), the SC/GC must collect assent from that child for the parent and child to continue in the study. Assent for randomization (i.e. Assent form 1) and assent for genomic sequencing (i.e. Assent form 2) are obtained by the SC/GC in the same manner as outlined above for obtaining parental consent for intervention 2. Further details on these tasks can be found in the "[Tracking System Tasks](#)" section on page 150. Assent forms are typically discussed once the parent consent process is complete. In rare occasions, assent form 1 is discussed after the parent signs the HIPAA consent form, and then assent form 2 is discussed after the parent signs the parent consent form 2.

These alternative time periods for obtaining assent are necessary because parents may be more interested in hearing about the second part of the study, while participants are tired and/or need time to become engaged in the process or are focused on the iPad/snacks. The SC should use their judgement as to when to begin the assent process. The SC should inform the parent of the timing of the assent process and check their agreement. If they agree, the SC can proceed with that timing. If there is disagreement, the SC should defer to the parents preferences.

Regardless of the timing of the assent process, the SC starts the process by re-introducing themselves to the participant. Then, the SC asks the participant if they have any questions about why they are seeing the SC or what they heard the SC discuss with their parent(s). After questions are answered, the SC tells the participant what will happen next (i.e. they will talk about the study by looking at the laptop and talking) and that they can ask the SC questions, their parent(s) questions about their talk with the SC or ask their parent(s) to call the SC if they have questions later. Then, the SC begins the assent process.

Note: The assent process should involve more discussion than a screen by screen review on the SC's laptop, especially with younger participants.

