If the participant signs assent form 1, they are told if they are in the group of kids that are asked to give a little bit of their blood (about 1-2 teaspoons) or if they are in the group of kids that do not have to do anything extra then what the doctor has already talked to their parent(s) about during their doctor's visit. The participant is asked if they have any questions, and if so, the questions are answered. Then depending upon the intervention 2 assignment the SC proceeds with assent 2 or with providing child and parent compensation as described [below](#).

Note: parent(s) are given a copy of the assent forms that are discussed with their child.

If the participant declines signing assent form 1, the SC informs the parent(s) and participant that study participation for intervention 2 cannot proceed. In the tracking system, the SC should exit (without saving) the current task and mark the participant "Refused" manually with the reason "Declined at Visit 1 – Intervention 2" and a short explanation.¹ Then the SC thanks the family for their time, provides parent and child compensation as described below, and escorts them to either phlebotomy (for provider bloodwork), check-out, or towards the appropriate hospital exit.

If the participant declines assent form 2, the SC informs the participant that no genetic sequencing will be done but the participant would continue to be in the NCGENES 2 study and the parent would be provided with follow-up surveys. Then the SC thanks the family for their time, provides parent and child compensation as described below, and escorts them to either phlebotomy (for provider bloodwork) or check-out, or towards the appropriate hospital exit. These participants will have a status of "Declined Consent/Assent to GS"

¹ See page 18 for more information on marking participants refused.

Cases of discordant consent/assent. If a child can assent to participate in Intervention 2, both the parent and child must agree to continue participation. Further, both parent and child must have concordant consent/assent for the check boxes related to the study's continued access to the child's medical records and for the disclosure of medically actionable secondary findings. If the child is 7 years or older chronologically and developmentally, the parent must consent AND the Child must assent for the participants (parent-child pair) to remain in NCGENES.

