If the consent and assent are discordant, a participant should be manually given the final status of REFUSED and a note detailing the reason for this change should be added to the participant's log in the study's tracking system.

Distribution of Parent and Child Compensation

At the completion of the consent/assent process parents will sign for compensation through the "Visit 1-Parent Reimbursement" task. For detailed instructions on this task see the "[Tracking System Tasks](#)" section on page 152. If the tracking system does not work, the SC will use a receipt book to complete this task. The study coordinator fills in the amount provided to the parent according to what was completed before and during visit 1. Child participants in the study will be offered a nonmonetary gift at the end of visit 1. For more information on participant compensation, see the "[Tracking Participant Compensation](#)" section on page 35.

Biospecimen collection

After the appropriate forms are signed (i.e. parental consent form 2 and if necessary, assent form 2) and the parent and child compensation have been distributed, the SC escorts the family to the phlebotomy area appropriate to that clinic. At UNC, the SC will direct the participants to UNC's Women's Hospital for phlebotomy check-in. If the patient is having provider bloodwork, the SC escorts the parent to the individual check-in area. If the patient is not having provider bloodwork, the SC escorts the family to the area where they can pull a number for general check-in. At Mission, the SC will direct the family to the phlebotomy area of the Mission Children's Hospital.

When the participant is called for blood draw, the SC should escort the family to the blood draw area and inform the phlebotomist of the need to use the research blood tubes immediately after the provider's blood order is filled. The SC will pass the phlebotomist the labeled research blood tube either right before they are to be filled or places them next to the tubes for the provider's bloodwork, depending upon the level of SC assistance needed.

SC assistance

When necessary, the SC assists the phlebotomist/parent in holding the child for blood draw, as well as trying to keep them calm for this procedure. Assistance is typically needed, however the SC should take care not to obstruct the phlebotomist.

See biospecimen protocol regarding sample labeling, collection, lab distribution, processing, and reporting.

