Remaining DNA can be used for future research with parental consent and in rare cases with required concordant child assent (which is obtained at the time of GS randomization consent/assent). DNA will be stored indefinitely, but linked data will be destroyed on the patient's 18th birthday rendering all remaining samples anonymized.

In some cases, the physician may determine that parental DNA confirmatory testing is needed to interpret the genomic sequencing results of the child. In this case, the genetic counselor or nurse notifies the family and the research team of the need to collect parental DNA. The research team contacts the patient's parent to let them know that parental/relative genetic testing consents and saliva kits are being mailed (one for each parent). The research study coordinator will wait approximately one week and phone the parents to consent them by phone, have them sign the consents and return them along with their saliva samples to the BSP lab in an addressed/postage paid envelope. Extra consents will be provided so that the parents may keep copy for their records. In rare cases other adult relatives may need to be tested. This will be determined by the ordering physician. NCGENES 2 will pay for additional confirmatory testing in the CLIA if the physician determines that it is necessary for the interpretation of the results for the child.

FIGURE 1. Overview of sample flow through study laboratories, molecular sign-out, CLIA confirmation, and reporting

Collecting Blood Samples at Visit 1

NCGENES 2 prioritizes collection of blood for research biospecimens. As often as possible, NCGENES 2 blood specimens will be collected immediately following Visit 1 from participants consented to exome sequencing. This section outlines the protocol for collecting blood samples at each NCGENES 2 site.

Pre-Visit 1: Preparation of the Blood Collection Kit

All sites will use a generally uniform procedure for preparing blood collection kits. A blood kit is created for each participant and clipped to that participant's folder for use in the clinic (see "[Preparation for Visit 1](#)" on page 22). In addition, a second blood kit (without forms) should always be brought to the clinic should a redraw become immediately necessary due to failed collection.

Kit contents

Each blood collection kit will include:

- 2 biohazard bags
- 2 purple top 3ml EDTA vacutainers (**ALWAYS CHECK EXPIRATION DATE**)
- 5 ID barcode labels (includes 1-2 extra)

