- ¹1 CLIA Molecular Genetics Test Request Form signed/provider-specific² – printed on white paper (See [Appendix XXXIV](#) on page 281)
- 1 BSP Requisition Form printed on blue paper³ (see [Appendix XXXIII](#) on page 279)

Kit assembly before the visit

Place print patient-specific barcode ID labels, both blood tubes, one folded biohazard bag and a folded Molecular Genetics Test Request Form and/or BSP Requisition Form into the second biohazard bag. ALWAYS bring a pair of gloves should you need to handle the blood tubes. A biohazard-labeled cooler bag should also be brought to the clinic appointment for transporting mailing blood tubes to the BSP post-Visit 1.

After the Visit: Collection and Distribution

Each site will follow a slightly different protocol for collecting and distributing blood samples. This section describes the protocol for creating a phlebotomy order, assisting with blood collection, assembling the blood collection kits, and distributing blood samples at each site.

University of North Carolina at Chapel Hill – UNC

Creating EMR Research Phlebotomy Order

Following reveal of randomization #2 to receipt of genomic sequencing and completion of GS consent, but prior to walking the patient to phlebotomy area, the study coordinator will complete an Epic EMR Research Phlebotomy blood draw order ONLY IF a Clinical Phlebotomy order has NOT been initiated by the physician. If clinical draw HAS BEEN ordered, then the research blood collection is piggybacked on the clinical draw. Detailed instructions for creating a blood draw order can be found in [Appendix XXVII](#) on page 263.⁴ EPIC orders require a 3-step process: 1) creation of the order, 2) approval by the ordering physician, and 3) approval by phlebotomist before the phlebotomist draws the blood.

Blood Collection

Once an order has been created, the SC should assist the participant and parent with navigating the process of the blood draw.

¹ **ONLY** for ECU and UNC. Mission creates Molecular Genetic Test Request electronically

² A UNC MGL form will need to be signed by each physician on the study team one time – then these can be photocopied for use throughout the study. The study coordinator will select the appropriate MGL/CLIA lab physician's form to include with the blood kit.

[figure not shown]
³ The BSP Requisition Form is printed on blue paper to easily distinguish which form is which when both are folded and placed in separate blood bags

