Scenarios 1 and 2 should be identified by the SC at the time of the blood draw. Scenario 3 will occur after the conclusion of Visit 1. The protocol in each scenario is described below.

Saliva Collection Initiated at Visit 1 Phlebotomy

Scenario 1: No Blood Drawn

The Study Coordinator may encounter a scenario in which blood collection fails entirely at phlebotomy or the parent declines blood draw for the child at Visit 1. In these cases, the parent is offered the option of saliva collection by mail. In the tracking system, this will be recorded in the “**Visit 1 Biospecimen Collection**” task (see page 154) with “Question 1. Blood collection Complete?” Answering this question “No” will autogenerate two tasks: “**V1 BSP Saliva Kit Due to No Blood Drawn**” (see page 156) and “**V1 CLIA Saliva Kit Due to No Blood Drawn**” (see page 155). Because DNA will be needed for both labs, two saliva kits are mailed to the parent.

Scenario 2: Insufficient Blood Collection at Visit 1

The Study Coordinator may encounter a second scenario of insufficient sample collection (<1ml in either tube). If this occurs the Study Coordinator will ask the phlebotomist to attempt to draw an additional tube (or attempt a second stick if the parent agrees) to see if enough blood may be collected to satisfy each lab’s requirements (at least 1 ml for each lab). If the phlebotomist is unable to obtain two 3ml tubes (or a set of 3 tubes that provides at least 1 ml for each lab), the Study Coordinator will inform the family that they will receive 1-2 saliva kits by mail depending on the need, e.g. if enough blood was collected (1 ml) to satisfy the needs of one of the labs, then only 1 kit would be needed (see **Saliva Collection section** on page 178). In the tracking system, this will be recorded in the “**Visit 1 Biospecimen Collection**” task (see page 154) with Questions 2-3. Answering Question 2 “No” will autogenerate the “**V1 BSP Saliva Kit Due to No Insufficient Sample**” task (see page 158) and answering Question 3 “No” will autogenerate the “**V1 CLIA Saliva Kit Due to Insufficient Sample**” task (see page 157).

Scenario 3: Saliva Collection Initiated by Lab (BSP/CLIA/Mission CLIA)

Failed Results

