If insufficient specimen is received by mail (either blood (<1ml) or saliva (<0.5ml)) in the lab(s) OR if DNA extraction fails to produce sufficient quantities of DNA for study needs at either lab, then the lab staff must notify [name], [contact] AND [contact]) and the Study Coordinator by email and phone ([name] [contact] AND [contact]) within 24 business hours of sample receipt/sample extraction failure to allow for recollection by saliva kit mailing. The UNC research team will notify the partner site if relevant and work together to ensure that the tracking system is updated and the saliva kit(s) are properly mailed (in most cases the UNC staff will be

¹ In some cases an extra tube or second stick (after the clinical draw) may be necessary to acquire a sufficient volume of blood, so the SC should always have an extra set of tubes/labels should this be necessary at blood draw

responsible for mailing saliva kit(s) to collect a pediatric patient's (Child's) specimen).¹ If the need for saliva collection arises after the conclusion of Visit 1, the study coordinator or other study staff under the direction of the study coordinator will notify the parent by phone of the need for a saliva kit collection. This contact is recorded in **communication log** in the tracking system. Additionally, the local Study Coordinator must record the failed results from blood collection (failed extraction/insufficient blood) reported by the lab(s) by creating "V1 BSP/CLIA Saliva Kit Due to Failed Results" task for one or both labs. For detailed instructions on how to create these tasks, see the "**Using the Tracking System**" section on page 75.

Note: ALL POST-VISIT 1 Phlebotomy sample scenarios such as insufficient samples received by mail and failed extractions are designated in the patient tracking system as FAILED RESULTS by Creating the V1 lab – saliva kit due to failed results task. Note to complete that task go to the task list for the patient and click 'pending', this will take you to a mail merge to create the label for the kit. Once the mail merge is completed the date associated with this task will be the date the kit was mailed.

Sample Fails Identity Check

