6. That we are seeing 850 kids and that we ask half the kids if we can look at their medical records until they are 18, and the other half of the kids we ask if we can look at their medical records and that they give a little extra blood (like 1-2 teaspoons). Giving this extra blood just means adding small tubes to the ones the doctor wants. They will not get stuck another time.
7. Us looking at their records does not mean they have to come back to see us, it just means work for us to do.
8. Ask if it's okay for you to flip the coin to see which group they are in
9. Pause and tell them which group they are in
10. Tell them the test is looking to see if there is a change in their genes that is the reason for why they came to clinic today.
11. The test will either say "yes" we see a change that is the reason, "no" we don't see a change that is the reason, or "we see a change" but don't know what it means. That we all have changes, and some cause people to come to the doctor and others don't.

Blood Draw:

- On side pocket of red bag are gloves and extra blood supplies.
- While family is waiting for blood draw to occur (or sooner if possible), do the following:
 - Label the tubes
 - In upper right- hand corner of the white provider signed MGL form, place study label and hand write date and time of blood draw
 - After tubes are obtained, complete the BSP form
 - After blood draw is done, walk them back to the area outside of phlebotomy and give them directions on how to exit the hospital. Then prepare the biohazard bags as below. If they valet parked, they go to either the hospital staff member at the front of the phlebotomy section or the information desk and they contact the valet service.
 - In one biohazard bag place the MGL form and the blood tube with the smaller amount of blood and send this bag to the CORE lab via the shoot system. Number for the core lab is 30. There is long delay between when select enter, for the tube to be sent and it actually goes. Stay there until the tube is gone and the screen is as it was before you sent the tube.
 - In the other biohazard bag, place the tube with the higher amount of blood and the completed BSP form into the red biohazard bag and take it to the BSP.
 - If needed help the parent hold/calm the child during blood draw.

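### The coordinator's assent talking point promises children no further needle stick and only added tubes, without condition, while the collection rules allow a second stick and a research-only draw

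*Protocol*

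**What the plan says.** **What the child is told.** Appendix IV, Study Coordinator list, Assent form 1 and 2, item 6, explains that half of the children are asked for a little extra blood and adds: "Giving this extra blood just means adding small tubes to the ones the doctor wants. They will not get stuck another time". The item has no branch for a child without clinical bloodwork and does not mention a repeat attempt. It comes before the coordinator asks leave to flip the coin (item 8) and reveals the group (item 9).

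**Who is told.** Under Obtaining assent in the Visit 1 procedures, for a developmental age of 7 or more, "the SC/GC must collect assent from that child for the parent and child to continue in the study". That section describes the sequencing group as children "asked to give a little bit of their blood (about 1-2 teaspoons") and makes no statement about needle sticks.

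**What the collection rules provide for.**
- Preparation of the Blood Collection Kit: "a second blood kit (without forms) should always be brought to the clinic should a redraw become immediately necessary due to failed collection".
- Saliva Collection for Child Participants, Scenario 2 (under 1 ml in either tube): the coordinator asks the phlebotomist to "attempt to draw an additional tube (or attempt a second stick if the parent agrees").
- Footnote to the overview of that section: "In some cases an extra tube or second stick (after the clinical draw) may be necessary to acquire a sufficient volume of blood".
- Biospecimen collection in the Visit 1 procedures: "If the patient is not having provider bloodwork, the SC escorts the family to the area where they can pull a number".
- Creating EMR Research Phlebotomy Order, in the same terms for UNC and ECU: a research "blood draw order ONLY IF a Clinical Phlebotomy order has NOT been initiated by the physician".
- The Mission coordinator checklist (Appendix XLII) lists a draw for research alone as the alternative to two additional tubes.

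**What the coordinator already knows.** Under RA Notifications, the research assistant must say whether the physician ordered bloodwork before the coordinator's part of the visit begins.

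**The concern.** The spoken item gives a child two assurances as fixed facts, and the same protocol contains procedures under which each is false. These children's own agreement is required, and the blood draw is the main physical burden that the sequencing arm puts on them. A coordinator who follows the item as written can tell a child that the study adds no needle when the study is the only reason for the needle, or that there will be no second stick when one may be requested minutes later. What is at stake is the accuracy of what a child hears before agreeing. No estimate, test or sample-size figure depends on it.

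**Working it through.** No arithmetic applies. The check sets the two assurances against the collection rules for each situation that a sequencing-arm child can be in.

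Assurance A: the research blood is only tubes added to the doctor's draw. Assurance B: no further stick.

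| Clinical blood ordered? | First draw gives at least 1 ml for each lab? | Assurance A | Assurance B |
|---|---|---|---|
| Yes | Yes | True | True |
| Yes | No | True of the first draw | Can fail: another tube is tried, or a second stick if the parent agrees |
| No | Yes | False: there are no doctor's tubes | Not contradicted: one stick in all |
| No | No | False | Can fail, as above |

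**Row 1** is the only case in which both assurances are certain to hold. It is the case in which the research tubes are taken along with the clinical draw and enough blood comes.

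**Rows 2 and 4** rest on Scenario 2 and the footnote. The footnote places the possible second stick after the clinical draw, which is the event that assurance B rules out.

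**Rows 3 and 4** rest on the general Visit 1 procedure, the UNC and ECU ordering rules and the Mission checklist. All of them provide for a draw when the physician has ordered none. That falsifies assurance A. It does not by itself falsify B, because there is no earlier stick for it to follow.

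**Who is affected in practice.** Both randomizations are 1:1 (Appendix III), so about half of the assenting children are not assigned to sequencing and have no research draw. For them the wording has no consequence. Within the sequencing arm, the children affected are those in rows 2 to 4. The protocol gives no rate for missing clinical orders or for tubes under 1 ml, and none is assumed here.

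**The volume.** The item's figure of 1-2 teaspoons agrees with the main-body assent description. It is not in question.

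**The case against.** The strongest reply is that this is a staff aid and not the assent document. Appendix IV is an activities list of prompts in the third person, and nothing requires them to be recited word for word. The child is taken through the assent forms themselves, whose text is largely not shown. Assent is typically discussed after the parent's consent is complete, so the family often knows the assignment by then. A second stick is a contingency: an extra tube is offered as the alternative, the parent must agree, and a saliva kit is available if blood is not obtained.

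Most of this stands and lowers the weight of the point. It does not make the wording true. The Obtaining assent section says that the process should be more discussion than a page-through of the form, above all with younger children. What the coordinator says therefore matters to what the child understands. An accurate form would not excuse a contrary spoken assurance.

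A reader might infer more than the documents support:
- *That redraws are planned as routine.* Only the spare kit is always carried. The footnote speaks of some cases.
- *That a research-only draw breaks the promise of no further stick.* It is a single stick and contradicts only the sentence about added tubes.
- *That every assenting child is misled to their cost.* Children not assigned to sequencing face no research draw.
- *That the assent itself is deficient.* What the forms say about needles cannot be seen, so this cannot be shown.
- *That the protocol errs by naming only the parent's agreement to a second stick.* It is silent on the child's agreement at that moment. Silence there is not a contradiction.

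**Conclusion.** Item 6 is wrong as written. Its second sentence conflicts with the provision for a second stick when a tube holds under 1 ml, and its first with the research-only draw. The consequence is confined to assenting children in the sequencing arm with no clinical blood order or an insufficient first draw, in unknown number. The conclusion needs no assumed rate. It assumes only that coordinators use the item broadly as it stands. Trial statistics are unaffected. This is a minor participant-protection correction to an internal inconsistency of wording and does not concern the trial's design. The main-body assent description makes no promise about sticks and needs no change.

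**What to change.** Reword item 6 so that the coordinator uses the bloodwork information already received from the research assistant:

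- If the doctor ordered blood: small tubes are added to that draw and no extra stick is expected.
- If the doctor ordered none: there is one needle stick for the study.
- In either case: if too little blood comes, a second try may be asked for, or a saliva kit used.

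Keep the 1-2 teaspoons. No new data, procedure or supplies are needed. The cost is two or three sentences in one talking point. The protocol does not say whether these prompts are under IRB control; if they are, a minor amendment is added. A few more declines or saliva kits are possible, and the documents give no basis for estimating how many.
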